#### D. Visit-specific procedures

##### Visit 1 – Approximately 2.0 hrs

Visit 1 is set up as a consenting visit. The coordinator will present a detailed review of the SARP consent and answer any questions regarding the study and study procedures.

This consent describes the national SARP group and the collective/common procedures, data sharing, sample sharing and genetic blood draw. A detailed medical and asthma history will be taken. Subjects will be given a brief physical examination that includes vital signs, height, weight, BMI and Tanner staging for children under the age of 17 (see Growth MOP). Subjects will also complete questionnaires (ACT/cACT, ACQ, and AQLQ/PAQLQ) and additional validated questionnaires. Females of childbearing potential will have a urine pregnancy test.

Baseline spirometry will be performed in all age groups. Spirometry will be performed before and after albuterol for all age groups and possibly ipratropium bromide for adults to determine maximum reversibility. A maximal reversibility must be completed within 6 weeks of Visit 2, either performed at this visit or at Visit 2.

If the subject has a previously documented methacholine challenge performed according to standard procedures from an NIH trial (SARP I or II, AsthmaNet, ACRN, or CARE), or the ALA-ACRC, he/she will not need to complete a methacholine challenge procedure.

Visit 1 can be split into several visits to complete screening based on site specific SOPs.

### **Visit 2 – Approximately 2.5 hrs**

At this visit, blood will be drawn for CBC with differential count, total IgE, ImmunoCap and isolation of DNA for SARP genetic studies to evaluate genes that may be related to the development of asthma, allergy and related diseases. Plasma and serum will be processed and saved for analysis. A urine specimen will be obtained from each individual for assessment of oxidative metabolites. Females of childbearing potential will have a urine pregnancy test. A brief medical history, adverse event and concomitant medication update will be conducted. The ACQ questionnaire will be administered. If pre- and post-albuterol spirometry has not been completed within the previous 6 weeks, or if the subject's medications have been changed since it was last done, it will be performed at this visit. In addition, a sputum induction will be conducted to evaluate airway inflammation on subjects age 12 and above. Exhaled nitric oxide will be measured, and exhaled breath condensate will be collected. After all procedures have been completed at this visit, subjects will then receive a single intramuscular injection of triamcinolone acetonide. If a procedure cannot be completed as planned, the injection should be rescheduled following the completion of the required procedures.

### **Visit 3 – Approximately 2.0 hrs**

This visit will be a repeat of procedures already completed and will occur within 18 days ( $\pm$  3 days) post Visit 2. These procedures include spirometry, maximum bronchodilation, a brief medical history, ACQ, adverse event and concomitant medication update, blood draw (for CBC with differential count, isolation of DNA for SARP epigenetic studies, plasma, and serum), urine and sputum (ages 12 and above) will be collected, exhaled nitric oxide will be measured, and exhaled breath condensate will be collected.

### **Visit 4 – Follow up visit at 12 months-post enrollment – Approximately 2.5 hrs**

This visit will be a full office visit with the research staff that occurs 12 months post enrollment  $\pm$  90 days, and can be split into two shorter office visits if more convenient for the subject and staff. A repeat of past procedures will be conducted and includes a detailed medical and asthma history update, a physical exam, spirometry, maximum bronchodilation, asthma questionnaires (ACT/cACT, AQLQ/PAQLQ, as well as other supplemental validated questionnaires used in baseline assessment (Epworth, ISI, HADS, MARS)), urine and blood collection, sputum induction (ages 12 and above), a urine pregnancy test for females of child bearing potential, measurement of exhaled nitric oxide and collection of exhaled breath condensate.

### **Visit 5 – Follow up visit at 24 months-post enrollment – Approximately 2.0 hrs**

This visit will be a full office visit with the research staff that occurs 24 months post enrollment  $\pm$  90 days, and can be split into two shorter office visits if more convenient for the subject and staff. A repeat of past procedures will be conducted and includes a detailed medical and asthma history update, a physical exam, spirometry, maximum bronchodilation, asthma questionnaires (ACT/cACT, AQLQ/PAQLQ, as well as other supplemental validated questionnaires), urine and blood collection, a urine pregnancy test for females of child bearing potential, and measurement of exhaled nitric oxide and collection of exhaled breath condensate.

### **Visit 6 – Follow up visit at 36 months-post enrollment – Approximately 2.0 hrs**

This visit will be a full office visit with the research staff that occurs 36 months post enrollment  $\pm$  90 days. A repeat of past procedures will be conducted and includes a detailed medical and asthma history update, a physical exam, spirometry, maximum bronchodilation, asthma questionnaires (ACT/cACT, AQLQ/PAQLQ, as well as other supplemental validated questionnaires), urine and blood collection (including CBC with differential count, plasma and serum), a urine pregnancy test for females of child bearing potential, and collection of exhaled breath condensate.

Additionally, blood collection at this visit will include the following:

- a. Measures related to metabolic health, including glucose, insulin, lipids, and HbA1c. Some of these measures (insulin, glucose) require a fasting blood sample, and so the blood draw at Visit 6 will be done under fasting conditions, where possible. A fasting blood draw will be an optional, not a mandatory, element of the protocol. Participants who typically have their visit in the afternoon (children especially) will not be able to fast. Therefore, this portion of the visit can be split out to a different day for these participants so that they can have blood drawn during a short morning visit after fasting
- b. Blood draw for study of RNA expression in blood cells using PAXgene.

### **Visit 7 – Long-Term Extension Annual Follow up visit – Approximately 2.5 hrs**

This visit will be a full office visit with the research staff that occurs annually  $\pm$  90 days. A repeat of past procedures will be conducted and includes a detailed medical and asthma history update, a physical exam, spirometry, maximum bronchodilation, asthma questionnaires (ACT/cACT, AQLQ/PAQLQ, as well as other supplemental validated questionnaires), urine and blood collection (including CBC with differential count, plasma and serum), sputum induction (ages 12 and above), a urine pregnancy test for females of child bearing potential, measurement of exhaled nitric oxide and collection of exhaled breath condensate.

### **Visits 8 and 9 – Long-Term Extension Annual Follow up visit – Approximately 1.5 hrs**

These visits will be full office visits with the research staff that occur annually  $\pm$  90 days. A repeat of past procedures will be conducted and includes a detailed medical and asthma history update, a physical exam, spirometry, maximum bronchodilation, asthma questionnaires (ACT/cACT, AQLQ/PAQLQ, as well as other supplemental validated questionnaires), blood collection (at either Visit 8 or Visit 9) and a urine pregnancy test for females of child bearing potential. The blood collection will include CBC with differential count, plasma and serum, PAXgene RNA and PAXgene DNA.

### **Follow up contact at 6, 18, 30, 42, 54, 66 , and 78 months-post enrollment – Approximately 0.5 hrs**

Subjects will be contacted at the above time points post enrollment (enrollment  $\pm$  60 days) listed to conduct a brief medical history, assess adverse events, administer ACT/cACT, and update concomitant medications. This contact will be made via a phone call to the subject. This contact will be important not only to get an update on the subjects well being but also to maintain contact throughout the longitudinal and long-term extension follow up portions of the study to retain as many subjects as possible. The 78-month phone contact will be for participants  $> 17$  years of age who will have the opportunity to enroll in the next phase of SARP.

## **E. Non-study drugs**

Because SARP is not a treatment trial, other drugs considered necessary for the subjects welfare may be given at any time. Participation in SARP will not prohibit access to new or novel therapies, but subjects will be asked to refrain from participating in a clinical trial involving biologic medications or other asthma therapies during the first year of SARP. Other participation in asthma clinical trials after the first year will be evaluated by the Steering Committee and if there is felt to be a potential adverse effect on the longitudinal protocol, these subjects will be discontinued. Medications will not be withheld except for the conduct of specific procedures such as spirometry and methacholine challenge as detailed in the accompanying MOPs.

## **F. Recruitment**

The study coordinator, the principal investigator or co-investigator will obtain informed consent in accordance with local IRB policies. This will be obtained before any testing is performed. The consent form contains language that describes the research nature of the study, the subject's ability to refuse to participate without any loss of health care. All of the risks (and benefits) associated with participation are delineated in the consent form. In addition, the coordinators and investigators will have been trained in the appropriate manner to obtain informed consent through IRB designated training programs.

Recruitment techniques will vary by study site and can include the use of physician-to-physician letters, physician-to-patient letters, newspaper advertisements, direct mail, television advertising, posted flyers in the local community and clinics, mass email to students/faculty, and the use of a recruitment database.

## **G. Drug supplies**

Triamcinolone acetonide (Kenalog® for injection) will be supplied by local pharmacies.

## **H. Education**

Standardized education about early recognition of asthma symptoms will be provided at each study visit. We will also reinforce the need for and use of individualized asthma action plans as well as the proper use of a pressurized metered dose inhaler (during spirometry sessions).

## **I. Retention**

Because this is a longitudinal study, some attrition is possible. Therefore retention efforts will focus on ease of visits and informational rewards (such as the asthma education). Visits will occur at times convenient to the subjects. We will make every effort to minimize parking problems and other general inconveniences. A monetary incentive will be given for each visit. Study staff will be available to answer questions about asthma and how to use the action plan. A study physician will be available by phone during off-hours to aid in management of asthma-related symptoms.

## J. Statistical considerations

Several of the hypothesis to be addressed by the SARP longitudinal study, described above, can be framed in terms of statistical tests of null hypotheses (e.g., “*the rate of lung function decline will be greater in subjects with severe versus non-severe asthma*”) while others can be framed in terms of model fitting (e.g., “*clinical composite phenotypes, such as the cluster phenotypes, will vary over the years of follow-up*”). The former will be examined in the broad framework of generalized mixed-effects linear models, which include familiar specific analyses such as: t-tests, logistic regression, Poisson regression and repeated measures ANOVA, among many others. The latter will be examined in the broad framework of structural equation models (SEM), which include familiar specific analyses such as: multilevel nested models, instrumental variable models, quantitative genetics models, longitudinal factor models and dynamic factor models.

Prior to analysis, individual outcomes will be characterized and examined for potential problems. Continuous data (e.g., FEV1, inflammatory cell markers) will be characterized by the sample mean, standard deviation and quartiles. Highly skewed measures may be log- transformed prior to analyses. Unacceptable data points may be identified as such on source documents (e.g., spirometry overread reports) or visual inspection and flagged as such. Categorical data will be characterized by frequency tables. Categories that occur rarely may be collapsed with other categories if it can be done in a way that is clinically meaningful.

As described above, some analyses will focus on narrowly defined tests of null hypotheses. In these cases, some patient characteristics expected to influence asthma outcomes, such as environmental exposures, treatments and co-morbidities, are not really of interest, but there is a need to adjust for them as likely confounders of the effect of primary interest. In this setting, propensity score based adjustments are often superior to covariate adjustment in the usual multiple regression approach. For other covariates that are not obvious confounders (e.g., clinical center), it may be possible to simply adjust for them as a way of reducing residual variability. For the analyses directed toward more general model-based hypotheses, some of these covariates may actually be endogenous to the model, meaning that they are both responses and predictors (e.g., asthma therapies), while other are strictly exogenous to the model, meaning that they are only predictors (e.g., sex, race, genotype). In this context SEMs are an effective approach for fitting models that can be interpreted clinically, but they also require substantial structure imposed, ideally based on clinical/scientific expertise and knowledge. Therefore, model selection will be both externally and internally (data) driven. The instrumental variable approach to model estimation will be utilized to determine whether or not a posited model is identifiable.

Although comparisons of the effects of different asthma treatments are not of particular interest in SARP, we anticipate that treatments will have effects and one complicating factor of the SARP design is that participants can choose to participate in randomized clinical trials, as provided for in section F. of the protocol. If we know which treatment a patient received while participating in a clinical trial, that information can be utilized in the same way as physician directed treatments self-reported by the patient at the regular follow-up visits and phone calls. Although we hope to determine which treatment was actually received by patient reports when the clinical trials is completed and that information is made available, there will certainly be cases where that information will not be available. However, we will know for certain which specific therapies the

participant might have received and the probability of each. For example, in a two-arm clinical trial we know that the probability for each therapy is 0.5. In this way, we can utilize the multiple imputation strategy to determine the degree to which the uncertainty is affecting the results of our models. Multiple imputation involves randomly assigning a specific treatment assignment to each data point where the treatment is unknown. The analysis then proceeds as if the treatments were exactly known. By repeating the process, we can then analyze the differences between the results to understand how the uncertainty in treatment assignment during the trial information introduces uncertainty in the results. Apart from the randomized treatment itself, participation in a clinical trial may also influence the asthma outcomes we are interested in because patients may have access to better care than otherwise would be available and will be factored into our models.

The total sample size target for the SARP longitudinal study is 700 subjects. Although some of the proposed analyses can be framed as statistical tests with associated type I and type II error rates, this sample size was not based on power considerations. The total budget for the SARP longitudinal study was set by the grant award. Thus, the total sample size is a direct function of the total budget and the per-subject cost for collecting outcome data. The SARP Steering Committee deliberated about the relative importance of obtaining specific outcomes both at baseline and longitudinally. The total sample size of 700 was chosen as the maximum that could be achieved with the minimal set of critical outcomes. For some of the simple analyses, such as t-tests, the power associated with this sample size will be very large for small effect sizes. Therefore, analyses will be interpreted using both p-values and confidence intervals to quantify the clinical relevance of the results. For the SEM based analyses, the value of this sample size is more difficult to characterize. Kim (*Structural Equation Modeling* 2005; v12(3); 368-390) discusses the relationship between goodness-of-fit indices, power and sample size in SEMs and concludes that the two existing methods of computing power based on noncentrality parameters cannot be implemented reliably. Others have proposed rules of thumb (e.g., 'the rule of 10') for choosing sample sizes relative to the model dimensions that are a function of the number of variables and parameters. The SARP Steering Committee believes that the total sample size of 700 will be able to support models with dimensions on the order of those that will be applied.

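### SEM structure may be chosen partly from the data on the full cohort, with no validation step, so apparent fit and any unadjusted inference for data-selected paths would be too favourable

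*Combined protocol and SAP*

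**What the plan says.** Section III.J divides the hypotheses into two kinds. Some are tests of null hypotheses and go to mixed-effects models; "others can be framed in terms of model fitting" and go to SEM. Its example of the second kind is the first sentence of hypothesis 7 (Section II), on change in cluster phenotypes. That hypothesis goes on to predict that specific genetic and pathophysiologic mechanisms determine the clusters and their change.

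On how a SEM will be specified, Section III.J says that "they also require substantial structure imposed, ideally based on clinical/scientific expertise and knowledge", and then: "Therefore, model selection will be both externally and internally (data) driven". No candidate structure, number of candidate paths, selection rule or stopping criterion follows. One check is named: "The instrumental variable approach to model estimation will be utilized to determine whether or not a posited model is identifiable".

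On sample size, it says "this sample size was not based on power considerations", and that the Steering Committee believes "the total sample size of 700 will be able to support models with dimensions on the order of those that will be applied". On interpretation, after a remark about simple analyses such as t-tests and just before SEMs are taken up, it says "Therefore, analyses will be interpreted using both p-values and confidence intervals to quantify the clinical relevance of the results".

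**The concern.** If the data help decide which paths stay in a model, and the same data are then used to judge those paths, the usual standard errors and fit indices lose their stated meaning. A path is more likely to be kept when chance has pushed its estimate away from zero, so retained estimates are too large, their intervals miss the truth too often, and the model appears to fit better than it would in new subjects. Identifiability is a different property: a model can be identifiable and still have been overfitted by selection.

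At stake are the mechanistic conclusions. Hypothesis 7 invites a large pool of candidate predictors: genotype is named as a predictor in Section III.J, and genome-wide data may be generated under Section III.C. Mechanisms picked out by the data could be reported as supported, with more certainty and better fit than they deserve.

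**Working it through.** **Inputs from the documents.** Seven clinical centers (Section I.A), about 100 subjects each (Section III.A), and a total of 700 (Section III.J). The total reproduces: 7 × 100 = 700. The plan gives no alpha, candidate count or error rate for the SEMs, so there is nothing further to reproduce.

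**Assumptions.** Two-sided 0.05 selection; K independent candidate predictors in one regression equation, standing in for one SEM equation; three true standardized paths of 0.10, the rest null; K = 5, 10 or 20.

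**Step 1: retention of a true path.** Expected z = 0.10 × √700 = 2.646. Probability of retention = Φ(2.646 − 1.96) = Φ(0.686) = 0.754.

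**Step 2: overestimation of a retained true path.** Mean z given retention = 2.646 + φ(0.686)/0.754 = 2.646 + 0.315/0.754 = 3.064. Ratio to truth = 3.064/2.646 = 1.16.

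**Step 3: coverage among retained paths.** A retained null path's nominal 95% interval excludes zero by construction, so its coverage is 0. A retained true path is missed only when its estimate is far too high (probability 0.025 per candidate), because estimates far too low are not retained. Hence

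coverage ≈ 3(0.754 − 0.025) / [3 × 0.754 + 0.05(K − 3)] = 2.187 / [2.262 + 0.05(K − 3)].

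| K | Arithmetic | By hand | Simulated, N = 700 |
|---|---|---|---|
| 5 | 2.187/2.362 | 92.6% | 92-94% |
| 10 | 2.187/2.612 | 83.7% | 84-85% |
| 20 | 2.187/3.112 | 70.3% | 69-70% |

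The simulated ranges come from two separate simulations, one with forward selection. Retained true paths were overestimated by 15-17%, in line with Step 2. If only the three true paths were candidates (K = 3), the formula gives 2.187/2.262 = 96.7%. Good prior structure therefore removes the coverage loss, though not the overestimation caused by the retention filter.

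**Step 4: fit.** With K = 20 null predictors, apparent R² averaged +0.008. With selection repeated and each center left out in turn, it averaged −0.010. The true value is zero, so the apparent figure is optimistic.

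**Step 5: can left-out path estimates serve as inference?** In null simulations, left-out estimates were pooled over centers for paths selected in all seven rounds. None of the pooled 95% intervals covered zero: 0 of 57 with 20 candidates and 0 of 138 with 40. Pooling over all seven centers nearly rebuilds the full-sample estimate that drove the selection. By contrast, selecting on 350 subjects and estimating on the other 350 gave coverage of 94.7-96.7% and a mean ratio to truth of 0.99-1.00. The price is power for a 0.10 path: Φ(0.10 × √350 − 1.96) = Φ(−0.089) = 46%, against 75% with all 700.

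**The case against.** The strongest case against has four parts.

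- **Path-level p-values are not promised.** The sentence on p-values and intervals follows the t-test remark and precedes the SEM discussion. A reader might infer that the plan will report p-values for selected SEM paths. The documents do not say so, and they name no p<0.05 selection rule. This stands, and the point is therefore conditional: any such inference, if unadjusted, would be optimistic. The remark about fit does not depend on that sentence.
- **Selection is also externally driven.** This stands as a limit on size: with few candidates and mostly prior structure, the effect on coverage is small. But clinical structure is described only as the ideal, and none is listed.
- **Large any-path error rates are multiplicity.** A reader might quote the chance of at least one false path among null candidates: 1 − 0.95^20 = 64%, or 1 − 0.95^40 = 87%. That does not show harm from selection. In simulation, backward elimination gave 64% and 87%, and a fully pre-specified model gave 64% and 89%. These rates should not be used here.
- **Context.** Section I.D says SARP is not a clinical trial, and Section V says the Manual of Procedures, which was not available, extends to the final statistical evaluation. Further detail may exist there. However, Section II presents these as hypotheses to be tested, and Section III.J neither labels the SEM results exploratory nor refers to a safeguard elsewhere.

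Use of the same subjects for selection and interpretation is itself inferred, from the reliance on all 700 and the absence of any split.

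**Conclusion.** The point holds in conditional form. Section III.J allows data-driven SEM selection on the full cohort and describes nothing that separates selection from interpretation. If it is followed as written, apparent fit is optimistic, and so is any unadjusted inference for data-selected paths. The direction is clear. The size cannot be derived from the plan: under the stated assumptions it runs from slight with 5 candidates to substantial with 20. The regression stand-in, independent predictors, 0.05 rule, K and path sizes are all assumptions.

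The null-hypothesis tests in mixed-effects models, such as hypothesis 1, are not affected, and paths fixed in advance are not affected to the same degree. The sample size need not change.

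**What to change.** In Section III.J, or in an analysis plan written before the SEMs are fitted:

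1. List the paths fixed in advance on clinical grounds, and keep ordinary p-values and intervals for those only.
2. State the rule by which the data may add or remove other paths. Label those paths, and their full-sample p-values, as descriptive or exploratory.
3. Repeat the whole selection with each of the seven centers left out in turn, and report out-of-sample fit and selection frequency beside the apparent fit. Use cross-validation folds instead where a measure is collected only at some centers, as with bronchoscopy, CT and MRI in Appendix 2.
4. Do not present pooled left-out path estimates as inference (Step 5 of the working). If confirmatory inference for a data-selected path is wanted, a split sample gives it, at the loss of power shown there.

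The cost is more computing, less favourable reported fit, and the loss of any claim that selected paths are confirmed. Each round selects on about 600 subjects. No new subjects, visits or measurements are needed.

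### Unknown trial treatments are to be imputed by a draw that, as described, ignores the outcome. Therapy coefficients and SEM therapy paths can then be biased, usually toward zero, and comparing imputations cannot show it.

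*Combined protocol and SAP*

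**What the plan says.** Section III.J (Statistical considerations) accepts that some participants will join randomized trials and that their treatment will not always be revealed: "there will certainly be cases where that information will not be available". For these cases it says it will still know the therapies a "participant might have received and the probability of each", and gives 0.5 per therapy in a two-arm trial as an example. The procedure follows: "Multiple imputation involves randomly assigning a specific treatment assignment to each data point where the treatment is unknown". Next, "The analysis then proceeds as if the treatments were exactly known". The process is repeated, and "we can then analyze the differences between the results to understand how the uncertainty in treatment assignment" feeds into the findings. The stated aim is to judge how far this uncertainty affects model results.

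Three other statements in III.J bear on the point:
- In the model-based analyses, "some of these covariates may actually be endogenous to the model, meaning that they are both responses and predictors (e.g., asthma therapies".
- Trial participation is to be modelled too, because "patients may have access to better care than otherwise would be available and will be factored into our models".
- For the narrower hypothesis tests, "propensity score based adjustments are often superior to covariate adjustment in the usual multiple regression approach". Comparing treatments is described as not a focus of SARP.

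No pooling rule is given, and no check against participants whose assignment is known.

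**The concern.** A valid imputation of a covariate that has its own coefficient in the outcome model must use the outcome. A label drawn only from the allocation probability is unrelated to the outcome within the trial. Analysed as if true, it adds records whose within-trial therapy slope is zero. The pooled coefficient is diluted, and part of the lost effect is credited to trial participation, the term meant to capture better care.

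The planned safeguard looks at differences between imputations. These show scatter around the diluted value, not its distance from the truth. Close agreement could therefore be taken as evidence that unknown assignments do not matter.

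Read literally, the draw is also made anew for each data point, so one participant could switch arms within a trial. That matters when a trial spans two or more data points. It is likelier for the ACT, which is also collected at the six-monthly calls (III.D).

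**Working it through.** **Inputs.** From III.J: N = 700, and allocation probability p = 0.5 in a two-arm trial. The documents give no therapy effect, trial uptake, unknown share or use outside trials, so these are assumed and varied. They state no bias figure, so there is nothing to reproduce.

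**Step 1: dilution.** Take a linear model with a participation term, use outside trials unconfounded, and the same effect β in known and unknown records. Let
- vT = share in trials × p(1−p)
- vO = share not in trials × r(1−r), where r is the rate of use outside trials
- u = share of trial labels unknown.

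Then the coefficient is b = β × [vO + vT(1−u)] / (vO + vT). With β = 0.50 and p = 0.5:

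| In trials | r | u | vT | vO | b, formula | b, simulated |
|---|---|---|---|---|---|---|
| 20% | 0 | 25% | 0.05 | 0 | 0.375 | 0.385 |
| 20% | 0 | 50% | 0.05 | 0 | 0.250 | 0.254 |
| 20% | 0 | 100% | 0.05 | 0 | 0.000 | −0.002 |
| 20% | 10% | 50% | 0.05 | 0.072 | 0.398 | 0.396 |
| 20% | 10% | 100% | 0.05 | 0.072 | 0.295 | 0.303 |
| 20% | 30% | 100% | 0.05 | 0.168 | 0.385 | 0.392 |
| 5% | 30% | 50% | 0.0125 | 0.1995 | 0.485 | 0.485 |

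The simulations used N = 700, 20 imputations pooled by Rubin's rules and 200 replicates.

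**Step 2: where the loss goes.** The participation coefficient shifts by (p − r)(β − b). For r = 0 and u = 50%: 0.5 × 0.25 = 0.125. For 20% in trials, r = 10%, u = 50%: 0.4 × (0.50 − 0.398) = 0.041. The shift is nil at r = 50% and slightly reversed above that.

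**Step 3: does the planned check see it?** Take 20% in trials, r = 10% and all trial labels unknown. At N = 700 the bias is 0.303 − 0.50 ≈ −0.20 and the between-imputation SD is 0.073. At N = 7000 the bias is still about −0.20, but the SD is 0.023. The spread shrinks with sample size and the bias does not. Confidence interval coverage falls from 76% to 0%.

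**Step 4: repeated measures.** Assumed: 7 annual points, 60% severe, uptake after year 1 of 30% (severe) and 10% (non-severe), three in-trial visits, ICC 0.6, 200 cohorts of 700.
- Therapy used only in trials, 25/50/75% unknown: 0.37/0.25/0.13 with one draw per participant, and 0.34/0.21/0.09 if redrawn at each data point.
- Half unknown, with 10/30/60% of the cohort using the therapy outside trials: 0.39/0.45/0.46.
- Low uptake (10%/3%) with outside use of 30%/10%, half unknown: 0.47, coverage 94%. Here the harm is negligible.

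**Step 5: SEM paths.** With 20% in trials, r = 10% and half unknown, a therapy-to-mediator path of −0.61 became −0.48, and a therapy-to-outcome path of 0.30 became 0.24. In a one-factor latent model with trial-only therapy and half unknown, a path of 0.50 became 0.25 and model fit did not worsen.

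**Step 6: direction.** If the slope outside trials (βO) differs from that inside (βT), then b = [vO·βO + vT(1−u)·βT] / (vO + vT). Blind draws remove part of the randomized information and keep the confounded part. In one constructed case with unmeasured confounding by indication, the coefficient moved from −0.22 (labels known) to −0.39. In another it moved from −0.21 to −0.29, and entering the allocation probability gave −0.34.

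**Step 7: contrasts of main interest.** With outside use dependent on severity, the severity coefficient moved from −0.503 to −0.474 (true −0.50). In the repeated-measures model (outside use 30%/10%, half unknown) the severe versus non-severe slope difference moved from −0.0296 to −0.0275, and its coverage stayed at 94–95%. Propensity-weighted severity contrasts stayed within 0.013 of the truth with participation in the score, and within 0.024 without it.

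**The case against.** The plan says treatment comparisons are not a focus, and none of the seven hypotheses in section II is a treatment effect. Therapy is mainly something to adjust for, often through propensity scores. A reader might infer that the severe versus non-severe results are compromised. The working does not support that, because those contrasts barely move. This part of the objection stands.

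Exposure is also limited. Joining a trial in year 1 ends SARP participation, and later participation is judged case by case (III.B, comment d). Participants may be discontinued if the protocol could suffer (III.E). Participants in trials may be spread over many agents, and a rarely used agent may not get its own term. The trial-only figures are therefore an upper end, not a forecast. This stands too.

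III.J may be a lay description of multiple imputation that leaves outcome conditioning implicit. A reader might infer that the plan rules such conditioning out. It does not; it names one basis for the draw and is silent on the outcome. That is reason to state the rule.

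Finally, a reader might infer that the estimate always shrinks toward zero. Step 6 shows otherwise when use outside trials is confounded, and III.J itself calls treatments likely confounders.

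None of this rescues the between-imputation comparison, which does not do what III.J wants of it.

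**Conclusion.** The concern holds in a conditional form. As naturally read, the draw ignores the outcome, and imputed records contribute a zero within-trial slope. A therapy coefficient or SEM therapy path is then pulled toward zero, provided that the effect is the same in known and unknown records, participation is in the model, and use outside trials has no unmeasured confounding. With such confounding it can move away from zero. The loss is about the unknown share for a therapy used only in trials, and much less when outside use is common or uptake is low. Since uptake and the unknown share are not given, the size ranges from negligible to complete loss.

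The harm is confined to therapy terms, the participation term and SEM therapy paths. The 0.5 in III.J is a loose example that assumes equal allocation, not an error of method. The point merits a short amendment and does not threaten the main hypotheses.

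**What to change.** Amend III.J to state:

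- (a) One assignment is drawn per participant per trial and carried through all data points in that trial.
- (b) The draw uses its probability given that trial's actual allocation ratio, the observed outcomes and the analysis-model covariates. Known assignments stay fixed, and results are pooled by Rubin's rules. In linear models, entering the allocation probability as the treatment value, with robust standard errors, is an alternative. State its limit: neither this nor any imputation removes confounding of use outside trials.
- (c) Results are compared with an analysis using only known assignments. A therapy's effect is reported as not identified where nearly all its labels are unknown and it is not seen outside trials.
- (d) The number of unknown assignments is reported by therapy and severity group.

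In 13 repeated-measures settings without unmeasured confounding, entering the probability gave 0.49–0.52 against a true 0.50 (coverage 90–96%), and outcome-conditioned draws gave 0.48–0.50 (92–96%). In the single-visit check (20% in trials, 10% outside), known assignments alone gave 0.496 with half the trial labels unknown and 0.512 with all unknown.

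The cost is modest. Outcome-conditioned draws need an imputation model per outcome and depend on that model being right. Entering the probability is simpler but less precise (SD of the estimate 0.107 against 0.094 with half unknown). Neither needs data beyond the allocation probabilities that the plan says it will have.
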